1.3.2.2 Summary of Clinical Safety

Doses administered in venetoclax clinical studies have ranged from 20 mg to 1200 mg.

As of 28 November 2018, on the basis of open-label and unblinded data available in the clinical databases for company-sponsored studies in the venetoclax oncology development program, a total of 2543 adult subjects (1313 CLL/SLL, 361 AML, 218 MM, 570 NHL, and 59 MDS, 20 ALL, 1 rhabdomyosarcoma, and 1 Evans tumor in the pooled analysis dataset across all monotherapy and combination therapy oncology studies in the venetoclax development program have been exposed to at least 1 dose of venetoclax. An additional 20 pediatric subjects (< 18 years of age; 5 ALL, 10 AML, 3 neuroblastoma, other solid tumors) have been exposed to at least 1 dose of venetoclax.

As of 28 November 2018, a total of 576 NHL subjects treated with venetoclax in the oncology clinical program had open-label or unblinded safety data available, including 136 subjects who received venetoclax monotherapy, and 440 subjects who received venetoclax in combination with other agents including rituximab, BR, R-CHOP, or G-CHOP. Fifty additional subjects received BR in Study BO29337. Of the 576 NHL subjects treated with venetoclax, 570 subjects are included in the pooled analyses across all studies, and data from the remaining 6 subjects

who crossed over to venetoclax treatment in Study BO29337 are excluded from the pooled analyses.

Overall for NHL, when treated with venetoclax as a single agent or in combination with other therapies, the most common adverse events were nausea, neutropenia, and diarrhea. Approximately three-fourths of subjects experienced ≥ Grade 3 adverse events, and the most common events were neutropenia, thrombocytopenia, and anaemia. The most common SAEs were febrile neutropenia, neutropenia, and pneumonia. Of the fatal events in the NHL program, the majority were adverse events of malignant neoplasm progression. Findings from the analysis based on the exposure-adjusted incidence rates were consistent with the findings from the analysis based on the subject incidence rates. Many of the adverse events reported in the current NHL studies are consistent with underlying disease or concomitant medical conditions, as well as other combination agents used to treat NHL patients. Safety in combination agents appears to be consistent with that observed in monotherapy trials and combination backbone regimen.

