9.2 Withdrawal from Study Treatment

Study treatment will be discontinued in the event of any of the following events:

- Progressive disease including clinical progression
- Unacceptable toxicity: an intercurrent illness or AE that prevents further ibrutinib or venetoclax administration
- Withdrawal of consent for treatment by subject
- Investigator decision (such as chronic noncompliance, significant protocol deviation, clinical deterioration, or best interest of the subject)
- Study termination by Sponsor
- Subject becomes pregnant

All subjects, regardless of reason for discontinuation of study treatment will undergo an End-of-Treatment Visit and, if applicable, be followed for progression and survival.

The investigator should notify the Sponsor within 24 hours if a subject discontinues study treatment (ibrutinib and/or venetoclax/placebo) due to disease progression and should provide documentation of disease progression for review by the medical monitor. If a subject shows signs of disease progression on physical examination or laboratory assessment, the subject may continue study treatment until disease progression is confirmed. These subjects should stay in the study to be followed for survival.

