11.1 Definitions

11.1.1 Adverse Events

An AE is any untoward medical occurrence in a subject administered a pharmaceutical product and which does not necessarily have a causal relationship with this treatment. An AE can therefore be any unfavorable and unintended sign (including a clinically significant abnormal laboratory finding, for example), symptom, or disease temporally associated with the use of an investigational study drug, whether or not considered related to the study drug (ICH-E2A 1995).

For the purposes of this clinical study, AEs include events which are either new or represent detectable exacerbations of pre-existing conditions.

The term "disease progression" should not be reported as an AE term. As an example, "worsening of underlying disease" or the clinical diagnosis that is associated with disease progression should be reported.

Adverse events may include, but are not limited to:

- Subjective or objective symptoms provided by the subject and/or observed by the investigator or study staff including laboratory abnormalities of clinical significance
- Any AEs experienced by the subject through the completion of final study procedures
- AEs not previously observed in the subject that emerge during the protocolspecified AE reporting period, including signs or symptoms associated with the underlying disease that were not present before the AE reporting period
- Complications that occur as a result of protocol-mandated interventions (eg, invasive procedures such as biopsies).

The following are NOT considered AEs:

- **Pre-existing condition:** A pre-existing condition (documented on the medical history CRF) is not considered an AE unless the severity, frequency, or character of the event worsens during the study period.

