11.4.2 Adverse Event Reporting Period

All AEs whether serious or non-serious, will be documented from the time the signed and dated ICF is obtained until 30 days following the last dose of study drug. SAEs will be reported to the Sponsor Drug Safety via an SAE reporting form and will be recorded in the eCRF from the time of ICF signing. Non-serious AEs will be recorded in the source documents from the time of ICF signing and will be recorded in the eCRF from the first dose of study drug.

Serious adverse events reported after 30 days following the last dose of study drug should also be reported if considered related to study drug. Resolution information after 30 days should be provided.

Progressive disease should NOT be reported as an event term, but instead symptoms/clinical signs of disease progression may be reported (see Section 11.1.1).

All AEs, regardless of seriousness, severity, or presumed relationship to study drug, must be recorded using medical terminology in the source document. All records will need to capture the details of the duration and the severity of each episode, the action taken with respect to the study drug, investigator's evaluation of its relationship to the study drug, and the event outcome. Whenever possible, diagnoses should be given when signs and symptoms are due to a common etiology (eg, cough, runny nose, sneezing, sore throat, and head congestion should be reported as "upper respiratory infection"). Investigators must record in the CRF their opinion concerning the relationship of the AE to study therapy. All measures required for AE management must be recorded in the source document and reported according to Sponsor instructions.

All deaths should be reported with the primary cause of death as the AE term, as death is typically the outcome of the event, not the event itself. Autopsy and postmortem reports must be

FINAL

forwarded to the Sponsor, or designee, as outlined above, if allowed per local regulatory guidelines.

If a death occurs within 30 days after the last dose of study drug, the death must be reported to the Sponsor as a SAE.

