The following safety analyses will be conducted to evaluate the use of venetoclax:

- Infectious pneumonia.
- TLS evaluated by adverse events of special interest and laboratory TLS per Howard criteria.
- Liver function abnormalities evaluated by laboratory data per Hy's law.
- GI Toxicities: No pooling will be done for diarrhea, nausea, and vomiting.
 - For each of the three preferred terms, events leading to treatment discontinuation and dose modification (dose reduction and/or dose hold) will be summarized.

 Table 3
 Summary of Safety Assessments

Assessment Type		
AE	TEAEs, SAEs, Grade 3 or higher TEAEs, related TEAEs, TEAEs leading to treatment discontinuation, TEAEs leading to dose reduction or dose hold, TEAEs leading to death, protocol-defined events of special interest defined by SMQ terms and other safety observations	Descriptive summary statistics and/or listings
Laboratory Parameters	Worst post-baseline toxicity grade for CTCAE-gradable hematology and chemistry results. Abnormalities in creatinine clearance, uric acid levels, and liver function tests. Laboratory TLS per Howard Criteria	Descriptive summary statistics and/or listings
Vital Signs and other Observations Related to Safety	Blood pressure, heart rate, temperature, and body weight, new or worsened eye-related symptoms	Descriptive summary statistics and/or listings

AE: adverse event; CTCAE: Common Terminology Criteria for Adverse Events; SAE: serious adverse event; TEAE: treatment-emergent adverse event; SMQ: standardized MedDRA (Medical Dictionary for Regulatory Activities) query.

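### Some lymphoma progression events and deaths can enter the by-arm SAE and fatal-TEAE rates, and the SAP does not separate them

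*Protocol*

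**What the plan says.** **What sites report at progression.** Protocol 11.1.1 states that the term for disease progression "should not be reported as an AE term". It then offers substitutes: a term saying that the underlying disease has worsened, "or the clinical diagnosis that is associated with disease progression should be reported". Protocol 11.4.2 reads: "Progressive disease should NOT be reported as an event term, but instead symptoms/clinical signs of disease progression may be reported", and refers the reader back to 11.1.1.

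**What sites report at death.** Protocol 11.4.2: "All deaths should be reported with the primary cause of death as the AE term". It adds: "If a death occurs within 30 days after the last dose of study drug, the death must be reported to the Sponsor as a SAE". Neither sentence makes an exception for death from lymphoma.

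**When treatment stops.** The first reason listed in Protocol 9.2 for stopping study treatment is "Progressive disease including clinical progression".

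**What is tabulated.** SAP Section 5 runs the treatment-emergent period to 30 days after last dose or the day before new anti-cancer treatment, whichever is earlier. Its TEAE definition excludes nothing for progression, and Protocol 10.6 includes all TEAEs. SAP Table 3 lists SAEs, Grade 3 or higher TEAEs, related TEAEs, TEAEs leading to discontinuation and "TEAEs leading to death". The only split of deaths is by COVID-19 (SAP 5.1). SAP Section 7 lists no change on this point.

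**The concern.** Progression is a component of the primary endpoint and the outcome that the plan expects to differ between arms. A lymphoma event recorded under another name, or a lymphoma death recorded under its cause, counts in the same aggregate rates that a reader uses to judge toxicity. If the combination delays progression, the control arm collects more of these events. A real excess of serious or fatal events on the combination then looks smaller than it is. Protocol 1.3.3.2 and 1.3.3.3 name neutropenia and serious infection as important identified risks of venetoclax, so the excess that could be diluted is a plausible one.

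The reporting rules also leave room for variation between sites. Faced with the same progression, one site may enter a disease-level term under 11.1.1 and another may enter a symptom, or nothing, under 11.4.2. Both would be following the protocol.

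**Working it through.** **Step 1: the route into the tables.**
- Progression ends treatment (Protocol 9.2), so it tends to fall near the last dose and inside the treatment-emergent window.
- If it is entered as worsening disease or as a diagnosis, it is a TEAE. It is also an SAE if it meets a seriousness criterion in Protocol 11.1.2.
- A lymphoma death within 30 days of last dose is an SAE by rule, with lymphoma as the term. If it falls in the treatment-emergent window, it is a fatal TEAE.
- No rule in SAP Section 5 or Table 3 removes or separates these events.

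**Step 2: the plan's own figure.** Inputs from Protocol 10.3: HR 0.61, medians 14 and 23 months, one-sided 0.025, 80% power, 1:1. Freedman's formula gives ((1 + 0.61)/(1 − 0.61))² × (1.960 + 0.842)² = 17.04 × 7.849 = 133.8, so 134 events. This matches the protocol and is not in dispute. The same assumptions are used below to gauge scale.

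**Step 3: PFS events by arm.** With exponential PFS, the proportion with an event by month t is 1 − exp(−ln 2 × t / median).

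| Month | Control (median 14) | Combination (median 23) | Gap (points) |
|---|---|---|---|
| 12 | 44.8% | 30.3% | 14.4 (before rounding) |
| 24 | 69.5% | 51.5% | 18.0 |

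**Step 4: the share recorded as SAE-type events.** The documents do not give this share f. It is assumed, and taken as equal in the two arms. At 12 months:
- f = 10%: 4.5 v 3.0 points of subjects, a tilt of about 1.4.
- f = 30%: 13.4 v 9.1 points, a tilt of about 4.3.

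**Step 5: overlap with other SAEs.** A subject who already has another SAE is not counted twice. If the two kinds of event are independent and the other-SAE rate is b in both arms, the net tilt is (1 − b) times the figure above:
- f = 30%: 0.6 × 4.3 = 2.6 points at b = 40%, and 0.4 × 4.3 = 1.7 at b = 60%.
- f = 10%: about 0.9 and 0.6.

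**Step 6: what a true excess would look like.** Assume other-SAE rates of 40% on control and 45% on the combination, a true excess of 5 points. The displayed rate in each arm is 1 − (1 − other rate) × (1 − f × PFS proportion). At 12 months:
- f = 10%: control 1 − 0.60 × 0.9552 = 42.7%; combination 1 − 0.55 × 0.9697 = 46.7%. Displayed excess 4.0 points.
- f = 30%: control 1 − 0.60 × 0.8656 = 48.1%; combination 1 − 0.55 × 0.9089 = 50.0%. Displayed excess 1.9 points.

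**Step 7: at the primary analysis.** SAP 1.5.1 plans about 150 PFS events. With 130 subjects per arm, uniform accrual over 21 months and no dropout, about 86 control and 64 combination subjects have an event (66% v 49%, gap 17.3 points). Assumed shares of 10%, 25% and 50% give tilts of 1.7, 4.3 and 8.7 points before overlap. Under the 40% v 45% illustration, the displayed excess becomes +3.7, +1.8 and −1.4 points.

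These figures show scale only. PFS events include deaths from other causes, and not every progression is serious or falls in the window. In this calculation, f has to absorb all of that.

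**The case against.** The strongest reply is that the protocol is less contradictory, and the SAP less blind, than it may look.

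- **The two sections overlap.** Both bar the literal term, and 11.4.2 cites 11.1.1 as its companion. A reader might infer that 11.4.2 confines sites to symptoms and signs. It does not: it says these may be reported, and elsewhere prefers diagnoses to symptoms where possible. The diagnosis meant in 11.1.1 can also be a complication of progression. This stands. What remains is a difference in the substitute term and in how binding it is.
- **Progression stays partly visible.** Protocol 10.6 summarises TEAEs by preferred term and by drug relationship, so a progression term has its own row. Related TEAEs are a separate item in SAP Table 3, and progression judged unrelated stays out of it. Listings or narratives may be provided for deaths and SAEs. Treatment disposition and discontinuation are tabulated (SAP 3.1). This stands, but the aggregate SAE and fatal-TEAE rates still mix the two kinds of event.
- **Safety is descriptive.** Protocol 10.6 plans no formal testing, so alpha, power and sample size are untouched. This stands.
- **The earlier programme proves little about this wording.** Protocol 1.3.2.2 says that, among fatal events in the venetoclax NHL programme, "the majority were adverse events of malignant neoplasm progression". A reader might infer that the present wording caused this. Those studies ran under other protocols whose reporting rules are not in the documents. The statement does show that such events can dominate a fatal-event count. It equally shows that they can be identified from coded terms.
- **Other influences on crude rates.** Longer exposure on the combination would also change TEAE proportions, and the calculation ignores it.

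**Conclusion.** The point holds as a gap in presentation. The protocol's rules let some progression events and lymphoma deaths into the aggregate SAE, Grade 3 or higher, discontinuation and fatal-TEAE rates, and the SAP does not pull them apart. If the combination prolongs PFS, the mixing adds more events to control and can dilute a true excess on the combination.

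The size is unknown because the recorded share is not in the documents. At assumed shares of 10% to 30%, equal in the arms, it is roughly 1 to 4 points at 12 months before overlap, and about 0.6 to 2.6 points after overlap at other-SAE rates of 40% to 60%.

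Two stronger readings are not supported. One is that the primary efficacy outcome as a whole enters the safety comparison: only events that are reported as AEs, fall in the window and, for the SAE table, meet a seriousness criterion do so. The other is that correcting 11.1.1 would cure the problem: the death rules in 11.4.2 would still put lymphoma deaths in the fatal-TEAE table.

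**What to change.** **Mainly in the SAP, before unblinding:**
- Fix a list of preferred terms that denote progression of MCL.
- In Section 5 and Table 3, present SAEs, Grade 3 or higher TEAEs, TEAEs leading to discontinuation and TEAEs leading to death by arm, both with and without those terms.
- Tabulate deaths by arm as progression versus other cause, with a row for unknown cause if needed. SAP 5.1 already separates deaths by COVID-19, so a split by cause is not new to the plan.
- Record the addition in Section 7.

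This uses data already collected. The cost is a term list and a few extra table columns. The full totals remain on display, so nothing is lost. SAP Section 1 says that the SAP is finalised before unblinding, which is the time to fix the list.

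**Separately, in the protocol:** reconcile 11.1.1 with 11.4.2 on what is reported in place of progression. A protocol change needs ethics approval (Protocol 12.14), so it belongs with the next amendment. It cannot alter events already recorded, and SAP Section 4 already gives a count of randomised subjects with ECOG 2 in the past tense. The SAP tables are therefore the essential part.

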3.1.2 Randomization Phase

The Randomization Phase portion of the study will follow a randomized, double-blind design. Ibrutinib and venetoclax/placebo will be administered using the Ramp-up Schedule that was determined to be appropriate for each TLS risk category. The Data Monitoring Committee (DMC) will review the safety recommendations made by the SRC and will be responsible for giving recommendations on continuing, modifying, or stopping the Randomization Phase of the trial (Figure 8).

Subject eligibility will be determined up to 28 days prior to randomization. Approximately 260 eligible subjects will be randomized at a 1:1 ratio to ibrutinib and venetoclax or ibrutinib and

placebo. Randomization will be stratified by number of prior lines of therapy, ECOG PS, and by TLS risk category.

Figure 8. Randomization Phase Schematic

Initially, subjects at increased risk of TLS will be hospitalized for a minimum of 24 hours (and up to 48 hours at the discretion of the investigator) at the start of the 20 mg ramp-up dose and again at the start of the 50 mg ramp-up dose of venetoclax for monitoring and prophylaxis of TLS. The DMC will review unblinded safety data during the course of the study to determine whether continued hospitalization of these subjects during ramp-up remains warranted.

Subjects will be treated with either ibrutinib and venetoclax or ibrutinib and placebo for approximately 104 weeks, followed by ibrutinib monotherapy until PD, unacceptable toxicity or withdrawal of consent. Venetoclax/placebo will be discontinued after 104 weeks of treatment regardless of response assessment.

Subjects who discontinue study treatment for any reason will be followed for progression (if not progressed before treatment discontinuation), subsequent anti-cancer therapy, and survival status until study closure.

[figure not shown]

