- Per protocol, pre-planned, or elective hospitalization: Per-protocol hospitalizations for TLS prophylaxis and management are not considered SAEs, unless a hospitalization is prolonged beyond 3 days due to an AE. A hospitalization planned before signing the ICF is not considered an SAE, but rather a therapeutic intervention. However, if during the pre-planned hospitalization an event occurs, which prolongs the hospitalization or meets any other SAE criteria, the event will be considered an SAE. Surgeries or interventions that were under consideration, but not performed before enrollment in the study, will not be considered serious if they are performed after enrollment in the study for a condition that has not changed from its baseline level. Elective hospitalizations for social reasons, solely for the administration of chemotherapy, or due to long travel distances, are also not SAEs.
- **Diagnostic Testing and Procedures:** Testing and procedures should not be reported as AEs or SAEs, but rather the cause for the test or procedure should be reported.
- Asymptomatic Treatment-related Lymphocytosis: This event should also not be considered an AE. Subjects with treatment-related lymphocytosis should remain on study treatment and continue with all study-related procedures.

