11.1.2 Serious Adverse Events

A SAE based on International Conference on Harmonisation (ICH) and EU Guidelines on Pharmacovigilance for Medicinal Products for Human Use is any untoward medical occurrence that at any dose:

- Results in death (ie, the AE actually causes or leads to death)
- Is life-threatening. Life-threatening is defined as an AE in which the subject was at risk of death at the time of the event. It does not refer to an event which hypothetically might have caused death if it were more severe. If either the investigator or the Sponsor believes that an AE meets the definition of life-threatening, it will be considered life-threatening.
- Requires in-patient hospitalization > 24 hours or prolongation of existing hospitalization
- Results in persistent or significant disability/incapacity (ie, the AE results in substantial disruption of the subject's ability to conduct normal life functions)
- Is a congenital anomaly/birth defect
- Is an important medical event that may not result in death, be immediately life-threatening or require hospitalization, but may be considered an SAE when, based upon appropriate medical judgment, the event may jeopardize the subject or

subject may require intervention to prevent one of the other outcomes listed in this definition. Examples of such events are intensive treatment in an emergency department or at home for allergic bronchospasm, blood dyscrasias, or convulsion that does not result in hospitalization; or development of drug dependency or drug abuse

Given that the investigator's perspective may be informed by having actually observed the event, and the Sponsor is likely to have broader knowledge of the drug and its effects to inform its evaluation of the significance of the event, if either the Sponsor or the investigator believes that the event is serious, the event will be considered serious.

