11.4.7 Adverse Events of Special Interest (AESI)

Specific AEs, or groups of AEs, will be followed as part of standard safety monitoring activities by the Sponsor. These events (regardless of seriousness) should be reported on the Serious Adverse Event Report Form and sent via email or fax to Pharmacyclics LLC Drug Safety, or designee, within 24 hours of awareness.

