- Within the first 24 hours after either the first dose or dose escalation, if any laboratory criteria below are met, the patient should be hospitalized for monitoring and the investigator notified. No additional venetoclax doses should be administered until resolution. A rapidly rising serum potassium is a medical emergency.
- Nephrology (or other acute dialysis service) should be contacted/consulted (per institutional standards to ensure emergency dialysis is available) on admission for any subject hospitalized prophylactically or in response to laboratory changes.
- IV fluids (eg, D5 1/2 normal saline) should be initiated at a rate of at least 1 mL/kg/hr rounded to the nearest 10 mL (target 150 to 200 mL/hr; not < 50 mL/hr). Modification of fluid rate should also be considered for individuals with specific medical needs.
- Monitor for symptoms or signs of TLS (eg, fever, chills, tachycardia, nausea, vomiting, diarrhea, diaphoresis, hypotension, muscle aches, weakness, paresthesias, mental status changes, confusion, seizures). If any clinical features are observed, recheck potassium, phosphorus, uric acid, calcium and creatinine within 1 hour STAT.
- Vital signs should be taken at time of all blood draws or any Intervention.
- The management recommendations below focus on the minimum initial responses required. If a diagnosis of TLS is established, ongoing intensive monitoring and multi-disciplinary management will be per institutional protocols

In addition to the recommendations in the table below:

- For potassium increase ≥ 0.5 mmol/L from baseline, or any value > 5.0 mmol/L, recheck potassium, phosphorus, uric acid, calcium and creatinine within 1 hour STAT and follow first guideline.
- For phosphorus increase of > 0.5 mg/dL AND > 4.5 mg/dL, administer phosphate binder and recheck potassium, phosphorus, uric acid, calcium and creatinine within 1 hour STAT.

Abnormality	Management Recommendations ^{1,2}
Hyperkalemia (including rapidly rising po	otassium)
Potassium ≥ 0.5 mmol/L increase from prior value (even if potassium within normal limits [WNL])	• Recheck potassium, phosphorus, uric acid, calcium and creatinine in 1 hour STAT. If further ≥ 0.2 mmol/L increase in potassium, but still < upper limit of normal (ULN), manage as per potassium ≥ ULN. Otherwise recheck in 1 hour.
	Resume per protocol testing if change in potassium is < 0.2 mmol/L, and potassium < ULN, and no other evidence of tumor lysis.

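### Protocol 11.1.1 and 11.1.2 classify a hospital stay of up to 3 days caused or extended by actual TLS in opposite ways, so SAE status and the 24-hour report depend on which section a site applies

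*Protocol*

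**What the plan says.** Protocol 11.1.1 lists what is not to be treated as an adverse event. Its item on per-protocol, pre-planned and elective hospitalization reads: "Per-protocol hospitalizations for TLS prophylaxis and management are not considered SAEs, unless a hospitalization is prolonged beyond 3 days due to an AE". The item then turns to stays planned before consent. For those, it says that an event "which prolongs the hospitalization or meets any other SAE criteria, the event will be considered an SAE".

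Protocol 11.1.2 gives the hospitalization criterion for seriousness: "Requires in-patient hospitalization > 24 hours or prolongation of existing hospitalization". It has no TLS exception and no reference back to 11.1.1. It also keeps the criteria of death, threat to life and important medical event, and adds that "if either the Sponsor or the investigator believes that the event is serious, the event will be considered serious".

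The planned prophylactic stay is in Protocol 3.1.2. At the 20 mg and 50 mg steps, subjects at increased TLS risk are "hospitalized for a minimum of 24 hours (and up to 48 hours at the discretion of the investigator".

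Appendix H, Section 1, covers what happens after a first dose or an escalation: "if any laboratory criteria below are met, the patient should be hospitalized for monitoring and the investigator notified". Its next instruction applies "for any subject hospitalized prophylactically or in response to laboratory changes", so it recognises two kinds of admission. Section 2 of the appendix directs admission for certain later potassium changes.

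SAE status triggers a report to the sponsor's drug safety group within 24 hours (11.4.3). Section 11.4.7 sets the same deadline for adverse events of special interest: "These events (regardless of seriousness) should be reported on the Serious Adverse Event Report Form". Major hemorrhage is the only such event that the protocol names (11.4.7.1).

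**The concern.** Exempting planned prophylaxis is reasonable: a scheduled stay in which nothing happens is not an untoward occurrence. The difficulty is the word management, which implies that there is something to manage. Because Appendix H makes admission for a laboratory change a protocol step, a site can reasonably file a stay for actual TLS as per-protocol management and apply the 3-day allowance. Another site can apply 11.1.2 to the same stay and report an SAE.

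The protocol treats TLS as an important identified risk of venetoclax, especially in CLL and MCL (1.3.3.1), and SAEs are a planned safety summary (SAP Section 5, Table 3). If classification depends on which section was read, the SAE tables are not comparable across sites, and some events that meet the protocol's own definition of serious miss the expedited report.

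**Working it through.** The documents give no figure to reproduce on this point. The check sets the two thresholds against the situations that the protocol creates, taking 3 days as 72 hours.

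| Situation | Under 11.1.2 | Under 11.1.1 | Conflict |
|---|---|---|---|
| Planned stay of 24-48 h, no event | Not an untoward occurrence | Exempt | None |
| Admission under Appendix H for actual TLS, more than 24 h and up to 72 h | SAE (over 24 h) | Exempt if read as per-protocol management | Yes: 72 − 24 = 48 h band |
| Planned 48 h stay extended by TLS, to at most 72 h | SAE (prolongation) | Exempt (not beyond 3 days) | Yes: up to 72 − 48 = 24 h of extension |
| Planned 24 h stay extended by TLS, to at most 72 h | SAE (prolongation) | Exempt (not beyond 3 days) | Yes: up to 72 − 24 = 48 h of extension |
| Any such stay prolonged by an AE beyond 72 h | SAE | SAE | None |

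Three further checks:

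1. **Does 11.1.1 repair itself?** The sentence that brings back prolongation and the other SAE criteria speaks of the pre-planned hospitalization and follows directly on stays planned before consent. TLS stays have their own rule, with a 3-day limit. If any prolongation already made a TLS stay an SAE, that limit would do nothing.
2. **Is there another route to a 24-hour report?** The special-interest route names only major hemorrhage. The remaining 11.1.2 criteria and the sponsor or investigator override do apply. Clinical TLS requires laboratory TLS plus raised creatinine, seizure, dysrhythmia or death (Appendix G), so severe cases may qualify that way. Laboratory TLS that resolves within 3 days is the group most exposed.
3. **How many events?** The documents do not say. Laboratory TLS was 1.5% to 2.5% in venetoclax NHL studies without ibrutinib (1.3.2.2). TLS occurred in 2 of 24 patients (8.3%) in the earlier ibrutinib-venetoclax MCL study (1.4.7): both among the 16 dosed before the starting dose was revised, none in the next 8 (1.4.2). As a rough scale, assume 260 / 2 = 130 subjects on venetoclax in the Randomization Phase. Then 130 × 0.015 = 2.0, 130 × 0.025 = 3.3 and 130 × 2/24 = 10.8 subjects with TLS. The share with a stay in the conflict band is unknown, so these are not counts of misclassified SAEs.

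**The case against.** The strongest reply is that nothing is concealed. Laboratory changes that need intervention are AEs (7.1.1.5), and all AEs are documented whether or not they are serious (11.4.2). The secondary endpoint concerns all TLS, not serious TLS (10.2.3). The SAP analyses TLS from AE terms and from laboratory data by the Howard criteria (Section 5). The DMC reviews TLS data (3.1.2, 5.3.2.2), and hospitalizations are collected as medical resource utilization (7.1.6). All of this stands. A reader might infer that real TLS admissions are hidden, or that the DMC sees too few cases among hospitalized subjects. The documents support neither inference, because the DMC's review is of TLS data and is not confined to SAEs.

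A reader might also infer that TLS resolving within 3 days escapes the run-in count as well. That is true only of laboratory TLS: the 72-hour condition in 3.1.1 does not apply to clinical TLS.

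It can also be argued that a stay for diagnosed TLS is not per-protocol at all, since Appendix H leaves ongoing management to institutional protocols and is titled as recommendations. That reading is possible. But the same appendix directs the admission itself, and the word management in 11.1.1 would then have little to cover. The ambiguity is the defect.

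Finally, the 3-day figure has a visible basis. Hospitalized subjects have Day 3 in-clinic dosing (8.2.1.3) and chemistry at 48 ± 2 hours as needed (7.1.1.10). This argues against replacing it with a shorter hour limit. It does not justify exempting a stay that TLS has caused or extended.

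**Conclusion.** The inconsistency is real and moderate. Followed literally, 11.1.1 withholds SAE status from TLS-caused admissions of more than 24 and up to 72 hours, and from planned stays that TLS extends within 3 days, while 11.1.2 confers it on both. At risk are consistent SAE classification, the 24-hour report and the SAE tables. The TLS endpoint and the PFS and OS analyses are not affected.

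This conclusion rests on two readings: that an admission directed by Appendix H can count as per-protocol management, and that the restoring sentence in 11.1.1 is confined to stays planned before consent. Both follow the text closely, though neither is the only possible reading. The prophylaxis half of the exemption is sound, and the number of affected events cannot be derived from the documents.

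**What to change.** Reconcile 11.1.1 with 11.1.2 and Appendix H in these ways:

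- Limit the exemption to planned prophylactic stays in which no TLS or other adverse event occurs. Define it by the event, with no new hour limit, so that an uneventful Day 3 stay remains exempt.
- State that an adverse event which causes an admission or prolongs a planned stay is judged by the ordinary 11.1.2 criteria.
- Before the CSR, use the existing AE and medical resource utilization records to identify TLS stays of 24-72 hours and check their classification. This matters because the SAP reports treatment-naive enrollment as complete (Section 1) and already cites a final-looking count of randomized subjects by ECOG status (Section 4). The wording still matters for new events, since ramp-up steps may be repeated after an interruption (5.3.2.5).

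Listing TLS under 11.4.7 would secure the 24-hour report for every case, but this is optional.

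The cost is an amendment to the wording, a limited record check, some additional SAE forms and a slightly less favourable SAE rate. Not every Appendix H trigger would add a form. One trigger is a potassium rise of at least 0.5 mmol/L within the normal range, and a trigger that is not an adverse event would not count. No dose or clinical management rule changes.
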